Telehealth CBT to increase engagement in pain treatment
among Veterans using prescription opioids

NCT05363176

June 30, 2023

Funding Agency: HSR&D

Principal Investigator: [name]

Abstract

Purpose: Chronic pain and negative consequences of long-term opioid therapy are related public health concerns associated with significant functional impairment, high psychiatric comorbidity, and premature mortality, particularly among Veterans. Clinical Practice Guidelines for opioid prescribing and pain management recommend using non-pharmacological approaches as first-line treatments. Psychosocial interventions (e.g., cognitive-behavioral therapy) have strong evidence supporting their ability to improve pain outcomes. Patient beliefs about the stigma associated with psychological interventions, opioid analgesics, ability of psychosocial intervention to improve pain among others can greatly interfere with the patients' ability to initiate and maintain engagement in psychosocial interventions and other non-pharmacological approaches.

Research question: Does Cognitive-Behavioral Therapy for Treatment Seeking (CBT-TS) increase treatment seeking of psychosocial and other types of pain treatments relative to a pain education control condition and what is the downstream impact on clinical outcomes?

Study Aims or hypotheses: The specific aims are to: test the effects of CBT-TS to increase initiation of psychosocial interventions for pain among Veterans receiving opioid analgesics for chronic pain (Aim 1); test the effects of CBT-TS to increase the retention in psychosocial interventions for pain among Veterans receiving opioid analgesics for chronic pain (Aim 2); and evaluate the effects of CBT-TS in improving pain and substance use outcomes among Veterans receiving opioid analgesics for chronic pain (Aim 3). We will also test the effects of CBT-TS on the initiation of and retention to other non-pharmacological pain treatments (Exploratory Aim).

Research Design Overview: Randomized Clinical Trial

Methodology: Participants (N = 300) will be randomized to either the CBT-TS condition or an education control condition. Participants in both conditions will complete assessments on pain, treatment engagement, and opioid use at baseline, and 1-, 3-, and 6-months post-treatments to assess primary, secondary, and exploratory outcomes. Treatment initiation and retention will be assessed primarily through data extraction and chart reviews. Participants will include men and women Veterans who: (a) are English-speaking, (b) are 18 years of age or older, (c) are taking at least 20 mg morphine equivalent daily dose of opioid analgesics per day for ≥ 90 days, (d) have pain that occurs on at least half the days for 6 months or more, and score ≥ 4 on each of the three items of the PEG. Veterans will be excluded on the basis of: (a) having used a nonpharmacological approach to pain management in the last 30 days, (b) having cognitive impairment, and (c) being in hospice, undergoing oncology treatment, or having a recent or upcoming surgery

Data Safety Monitoring Plan: To ensure safety of participants in the study proposed and validity and integrity of data collected, the PI ([name]) will oversee all data and safety monitoring functions and the research team will be advised that he will be the primary contact overseeing these activities. The investigators will meet regularly to monitor study progress and discuss the implementation of monitoring procedures. He will also meet regularly with the research coordinator and staff to review monitoring procedures and ensure all efforts are being taken to minimize risks to participants. A Data Safety & Monitoring Board was not required by VA HSR&D.

Data Analysis: Aim 1 Hypothesis: A Cox Proportional Survival Analysis will be conducted to examine treatment initiation by the 6-month follow-up. Condition will be entered into the model as a predictor of whether a participant reported attending treatment by the 6-month follow-up. A secondary logistic regression analysis will be conducted to examine treatment initiation by the end of the 6-month follow-up using worst case imputation of missing outcome to test robustness of any effects. **Aim 2 Hypothesis:** The outcome will be sessions of psychosocial pain treatment attended during the 6-month follow-up period. Analyses will be conducted using MRM within a multilevel modeling (MLM) framework as this method allows for appropriate modeling of the covariance matrix when measures are repeated over time and can easily account for normal, skewed, and categorical data. MRM will be used, including treatment condition, follow-up time (centered on 6-month follow-up), and a condition by time interaction term as predictors of number of sessions of treatment attended. **Aim 3 Hypotheses:** The outcomes will be pain severity, pain interference, physical functioning, opioid dose, and risk of misuse. MRM will again be used. Treatment condition, follow-up time (centered on 6-month follow-up), and a condition by time interaction term will be included as predictors as will the relevant baseline autoregressors. Additional secondary analysis to demonstrate treatment robustness will involve centering time at the 1-month and 6-month follow-ups, allowing for examination of treatment differences at these timepoints.

List of Abbreviations

ACT – Acceptance and Commitment Therapy

ASSIST – Alcohol, Smoking, and Substance Involvement Screening Test

BHS – Beck Hopelessness Scale

CBT – Cognitive Behavioral Therapy

CoE – VISN 2 Center of Excellence for Suicide Prevention

COMM – Current Opioid Misuse Measure

CPG – Clinical Practice Guidelines

ITT – Intent-to-treat

MAR – Missing at random

MBQ – Medication Beliefs Questionnaire

MBSR – Mindfulness-based stress reduction

MCAR – Missing completely at random

MEDD – Morphine equivalent daily dose

OD – Opioid use disorder

PCS – Pain Catastrophizing Scale

PROMIS – Patient Reported Outcome Measures Information System

PSEQ – Pain Self-Efficacy Questionnaire

PTWS – Pain Treatment Willingness Scale

SEM – Structural Equation Modeling

SBIRT – Screen, Brief Intervention, and Referral to Treatment

TSK – Tampa Scale for Kinesiophobia

2.0 Introduction

Chronic pain is a significant public health problem. In the United States, the estimated annual cost burden of chronic pain on healthcare, disability, lost wages and productivity exceeds \$500 billion.¹ Low back pain, neck pain, and other musculoskeletal conditions are each among the leading contributors to disability.² Veterans are vulnerable to develop chronic pain¹ and report higher pain severity relative to the general population.³ Health record data from the Veterans Health Administration (VHA) indicate that 55% of almost 10 million Veterans in VHA care between 2000 and 2011 had a diagnosis of a musculoskeletal condition.⁴ Veterans with pain conditions report poorer psychosocial functioning, exhibit high rates of psychiatric and medical comorbidity, and are at increased risk of suicide.^{4,5}

Opioid misuse: A National Public Health Emergency. There is overwhelming evidence of premature mortality and other significant adverse outcomes associated with opioid analgesic use.⁶ There were nearly 50,000 opioid overdoses in the United States in 2019 representing greater than a 4-fold increase from 2002.⁷ Suicides involving opioids nearly tripled from 1999 to 2014.⁸ Studies among Veterans indicate that higher doses of opioid analgesics increase risk of suicide,⁹ and overdose risk is increased by over seven-fold with higher doses of opioid analgesics.¹⁰ Longitudinal studies indicate that long-term opioid analgesic use (i.e., greater than 90 days) is associated with depression onset and recurrence,^{11,12} the development of opioid use disorders, and aberrant drug-related behaviors (e.g., illicit substance use, alternative routes of administration)¹³ among individuals experiencing chronic pain.

Overall, the long-term use of opioid analgesics to manage chronic pain is guided by little evidence and is associated with increased morbidity and mortality. In most cases, safe and effective alternatives to opioid analgesics are preferred in managing chronic pain.^{14,15} Many non-pharmacological pain treatments have good evidence and are associated with lower risk and similar, if not greater, potential for improvement.¹⁶ There is a need to identify ways to engage Veterans in non-pharmacological pain treatment prior to the onset of the adverse outcomes of opioids, after the onset of adverse outcomes, or even prior to starting opioid analgesics to prevent the poorer prognosis associated with long-term opioid analgesic use.

Using psychosocial pain treatments to reduce reliance on opioid analgesics. The VA/Department of Defense Clinical Practice Guidelines (CPGs) for opioid prescribing^{14,15} recommend non-pharmacological pain treatments as first-line. Among the many non-pharmacological strategies, psychosocial pain treatments—Cognitive-Behavioral Therapy for Chronic Pain (CBT-CP), Acceptance & Commitment Therapy (ACT), Mindfulness-Based Stress Reduction (MBSR)—offer a solid evidence base, promote active participation in care, and emphasize the psychological and social factors that are often neglected in the biomedical intervention of long-term opioid therapy. Psychosocial pain treatments reinforce skills to address negative emotions, and maladaptive thinking and behavioral patterns that impact pain.¹⁷ They are also particularly helpful in opioid tapering and discontinuation.¹⁸

Psychosocial pain treatments are effective for improving pain outcomes.¹⁹ CBT-CP reduces pain interference by changing maladaptive thinking patterns, increasing activity level, and improving mood.²⁰ Importantly, across different types of pain, meta-analyses and studies on randomized clinical trials indicate that CBT-CP has strong effects on mood, pain interference, pain severity, and pain catastrophizing compared to non-active controls.^{17,21} ACT targets harmful avoidance of experiences (e.g., sensations, thoughts, behaviors), while encouraging acceptance of one's pain and staying in the moment to help Veterans make choices that are consistent with their values. Again, meta-analyses support medium effects on mental and physical health functioning and improved pain outcomes that are comparable to CBT-CP.^{22,23} For MBSR, meta-analyses show improvements in pain, depression, pain intensity, physical functioning and quality of life outcomes.^{24,25} A large randomized clinical trial also found that MBSR demonstrated clinically meaningful improvements in disability that was comparable to CBT-CP and better than usual care.²⁶ Taken together, psychosocial pain treatments are considered first-line interventions that demonstrate positive outcomes.

There are also apparent disparities in some demographic groups. For example, racial/ethnic minorities relative to those who are White non-Hispanic are under-engaged in pain treatment

despite often reporting higher pain severity and greater interference in activities.³⁹ Among the general population, adults 65+ years are more than twice as likely to have prescription opioid fills and have had the smallest decline in prescriptions over time.⁴⁰ They also tend to underutilize CBT-CP and exercise for managing pain and are less likely to have a history of using complementary and integrative health services.^{41,42} While women are more likely to receive non-pharmacological pain treatment, they are also more likely to receive opioid analgesics and be co-prescribed sedatives increasing the risk adverse outcomes.^{40,43}

Barriers of treatment engagement include lack of patient and provider knowledge, poor patient-provider communication, and lack of access and availability.^{19,44} Efforts have been led to improve patient-provider communication^{45,46} and provider education.⁴⁷ To combat access and availability barriers, the Comprehensive Addiction Recovery Act (CARA) required that interdisciplinary pain care teams have access to psychosocial pain treatment, in addition to other non-pharmacological pain treatments (e.g., complementary and integrative health approaches).⁴⁸ National dissemination of CBT-CP training has increased the number of providers who deliver CBT-CP.³⁰ According to the 2019 Pain Management in VHA Survey Report, CBT, ACT, and MBSR were available in 98%, 79%, and 71% of facilities, respectively, demonstrating wide availability across the country.⁴⁹ Psychosocial pain treatments can easily be delivered through telehealth (offered at 79% of VHA facilities according to the survey administered pre-COVID).^{49,50} This is critical in increasing access for those who have mobility issues, have rural residence, and/or lack transportation.⁵⁰ Telehealth delivery also facilitates social distancing measures to reduce the spread of COVID-19.⁵¹ While efforts addressing educational, logistical, and communication barriers are essential, patient beliefs represent another critical barrier that has not received sufficient attention.

Beliefs serve as potent obstacles to engage in psychosocial pain treatments. Beliefs about opioids, non-opioid treatment, the potential of pain severity and interference to change, and stigma all have a profound impact on treatment engagement. Beliefs about opioids reinforce continued use, while reducing the likelihood of trying psychosocial pain treatments and other non-pharmacological approaches. A qualitative study found that some patients fear uncontrolled pain that is “impossible” to cope with without opioids.⁵² Krebs et al.⁵³ found that Veterans recruited for a pain trial perceived opioid analgesics to be more effective than non-opioids at baseline, despite no differences in pain after the trial was completed.⁵⁴ Many patients believe that prescription opioids are the most effective treatment and higher doses are needed for adequate pain relief, which mediates prescription opioid misuse.⁵⁵ On the other hand, some Veterans are reliant on their opioids and request dose escalations despite being ambivalent about their benefits and disliking side effects.⁵⁶

In addition to beliefs about opioids, people with chronic pain believe that they will be stigmatized if they use psychosocial pain treatments (e.g., people will think I’m crazy).^{50,57} Like mental health treatment, Veterans may perceive that they are weak, discriminated against, and judged by others.⁵⁸ Other beliefs relate to concerns about pain being dismissed as not actual physical pain if they receive psychosocial pain treatments, which would then be confirmed in their minds if the treatment worked to reduce pain.⁵⁷ People also indicate that because they experience pain solely as being physical, only medications or surgery can address it.^{50,57}

Pain catastrophizing, which includes helplessness over one's pain (e.g., "There's nothing I can do to reduce the intensity of the pain") is a critical factor that impacts engagement in coping behaviors, treatment adherence, and exercise.⁵⁹ Other factors are important in non-initiation and problems with retention of non-pharmacological pain treatments, including low pain-related self-efficacy (e.g., "I can't cope with pain without medications") and fear-avoidance beliefs (e.g., "I'm afraid I will injure myself if I start a walking program").^{60,61} Many also believe that non-pharmacological pain treatments lack efficacy, are time consuming, and increase pain or cause harm.⁴⁴ For MBSR, patients often cite that they "have no time," they are not aware of potential benefits, and the practices cannot be done because of lack of fitness or ability.^{62,63} Additionally, some patients become hopeless and fearful that there are not any treatments that can improve their pain.⁶⁴

Beliefs about treatment may vary as a function of demographics such as racial/ethnic minority status, gender, and age. Racial/ethnic minorities often report believing that pain is a sign of weakness, that pain is inevitable, and that they do not want to be labeled as complainers.³⁹ Similarly, many older adults believe that showing pain is a sign of weakness and that "treatments won't work."^{42,65} Some studies did not find differences in perceived barriers and facilitators of pain treatment engagement among men and women Veterans;^{44,66} however, one study found that women identified specific challenges of being female that interfered with treatment engagement. These beliefs included feeling like were not understood or believed by their providers, and that providers perceived that weight was a more central issue to their pain by relative to men.⁶⁷

Overall, beliefs can drive powerful negative emotions (e.g., despair, anxiety, hopelessness) and problematic behaviors (e.g., avoidance) that perpetuate functional impairment and continued use of opioids, despite harm, potential for harm, or lack of improvement. Evidence-based interventions are needed to directly address these patient beliefs that are potential barriers to engaging in psychosocial pain treatments.⁶⁸

CBT is ideally suited to modify beliefs interfering with engagement in psychosocial pain treatment. The mechanism behind CBT's efficacy comes from its demonstrated ability to change beliefs, which serves to change behavior (in the case of the current study, treatment initiation and retention).⁶⁹⁻⁷¹ CBT is effective for a wide range of conditions,^{21,69,72} is efficacious when delivered via telehealth,⁷³ and can be administered by individuals other than highly trained mental health professionals.⁷⁴ [name] (co-I) has developed CBT for Treatment Seeking (CBT-TS), which specifically targets treatment beliefs that interfere with treatment seeking. CBT-TS is backed by strong evidence that it increases treatment initiation and retention through changing beliefs. The current study will address the need of increasing the initiation of and retention to psychosocial pain treatments by modifying beliefs that are interfering with treatment engagement.

Conceptual Model. CBT-TS targets beliefs interfering with engagement, which will include beliefs about opioid analgesics, exaggerated negative thoughts about one's ability to address pain (i.e., helplessness-related catastrophizing, fear-avoidance beliefs, pain-related self-efficacy), and psychosocial and other non-pharmacological pain treatment. CBT-TS may also

increase the belief that they can manage their pain providing hope that their functioning can improve. By addressing such beliefs (e.g., “opioids are the only thing that helps me sleep”), patients will be more willing to engage in psychosocial pain treatments. Treatment engagement will then reduce their reliance on opioids as well as improve physical functioning, reduce pain severity, and pain-related interference in activity. CBT-TS may also change beliefs about a wide range of treatments including other non-pharmacological pain treatments and non-pain treatment (e.g., SUD, mental health), which may also impact downstream clinical outcomes.

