Paykel Suicide Scale (PSS)	X	X
UCLA Loneliness Scale	X	X
Other key measures		
Other relevant treatment utilization	X	X
Possible OUD, other SUD (ASSIST)	X	X
Anxiety and depression (PROMIS-29)	X	X
Optional Add-on Study Assessments		
Race-Related Events Scale (RES)	X	X
Discrimination in Medical Setting (DMS)	X	X
Racial Trauma Scale-Short Form (RST-SF)	X	X

Tampa Scale for Kinesiophobia (TSK). The TSK-11 is an 11-item measure assessing pain-related fear of movement or injury. Research supports the scale’s psychometric properties.⁸⁵

Loneliness: The 20-item Revised UCLA Loneliness Scale will be used to assess loneliness as both a clinical outcome and factor that may interfere with treatment engagement.⁸⁶

Suicidal thoughts and behaviors: For the 5-item Paykel Suicide Scale,⁸⁷ respondents will be asked to indicate (yes or no) if they had: (1) felt that life was not worth living, (2) wished, (3) thought about, (4) seriously considered, and/or (5) attempted suicide in the past year (at baseline)/since last visit (for all other assessments). Participants receive a score equal to the greatest magnitude of suicidal ideation or behavior positively endorsed.

PROMIS-29. The PROMIS-29⁸⁸ provides a profile of one’s health-related quality of life. Components of the profile include pain (severity and interference) and physical functioning. Anxiety and depression components will provide key data to account for mental health distress. The PROMIS-29 will also provide data on fatigue, sleep, and functioning in social roles. Pain intensity and interference is rated on a scale from 0 to 10 with greater scores indicating greater pain severity and interference in activities due to pain, respectively. The remaining scales are on a 1 to 5 rating scale with higher scores indicating greater problems.

Current Opioid Misuse Measure (COMM). The COMM is a 17-item measure that will be used to assess the frequency of aberrant drug-related behaviors and other behaviors that are prevalent among pain patients who are misusing prescription opioids (e.g., frequent visits to the emergency department). The rating scale on the COMM ranges from 0 (“Never”) to 4 (“Very Often”), with higher scores indicating greater risk of misuse of prescription opioids. The COMM has demonstrated strong psychometric support.⁸⁹

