Exploratory Analyses: Explore the effect of CBT-TS in increasing the initiation of and retention to other non-pharmacological pain treatments among Veterans receiving opioid analgesics for chronic pain. For treatment initiation and treatment retention, we will employ the same approach as described in Aims 1 and 2. As an additional set of exploratory analyses and consistent with an experimental therapeutics approach, we will explore beliefs as potential mediators of treatment initiation. Structural equation modeling (SEM) will be used to conduct these analyses. Latent variables (BHS, PTWS, PSEQ, PCS, TSK, MBQ, BQ) will be constructed to capture beliefs about opioids, treatment, beliefs that pain can be reduced, and hope. These variables will be included as potential mediators between condition and treatment initiation by month 6 as well as pain and opioid clinical outcomes at month 6. Prior to testing the mediation model, the direct effects of condition on treatment initiation, pain, and opioid outcomes at month 6 will be examined in one model. Next, the latent belief factors at month 3 will be included as mediators. All models will be conducted including relevant baseline autoregressors. Measurement invariance across conditions and across treatment initiation status will be established for the month 3 latent belief factors. All models will be re-analyzed using manifest variables instead of latent variables to test for model robustness. Any differences will be discussed. We will also explore variables such as gender, baseline dose, age, race/ethnicity, parent station type (1a-c, 2, 3) as potential moderators of treatment effect to drive further study.

Analysis in Support of Specific Aims for Optional Add-on Study: **Aim 1 Hypothesis:** African American participants receiving CBT-TS will be significantly more likely to initiate psychosocial pain treatment than African American participants in the control condition, compared to rates of treatment initiation in the rest of the sample. Treatment initiation of psychosocial pain treatment will be treated as a binary outcome variable (0|1). A Cox Proportional Survival Analysis⁹⁷ will be conducted to examine treatment initiation by the 6-month follow-up. Race will be dummy coded (0 = African American, 1 = other) and included as an independent variable as well as moderator of treatment condition.

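### The exploratory belief-mediation models name only baseline autoregressors as covariates, so the non-randomised path from beliefs to outcome is open to confounding by factors the trial already measures

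*Combined protocol and SAP*

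**What the plan says.** Section 2.0, Introduction, supplies the background rationale: CBT's "demonstrated ability to change beliefs, which serves to change behavior (in the case of the current study, treatment initiation and retention".

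Section 5.7, Exploratory Analyses, states: "we will explore beliefs as potential mediators of treatment initiation". Latent belief factors built from the belief instruments enter "as potential mediators between condition and treatment initiation by month 6 as well as pain and opioid clinical outcomes at month 6". The timing is fixed: "Next, the latent belief factors at month 3 will be included as mediators". The stated adjustment is one sentence: "All models will be conducted including relevant baseline autoregressors". The only robustness checks named for these models are a re-analysis with manifest variables and measurement invariance.

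Three other places bear on the choice of covariates.

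- Section 5.5 says of PROMIS-29: "Anxiety and depression components will provide key data to account for mental health distress". No model in 5.7 names these scores. The same section describes "loneliness as both a clinical outcome and factor that may interfere with treatment engagement"; loneliness also enters no model.
- The Introduction says treatment beliefs may vary with race/ethnicity, gender and age, and that treatment use differs across the same groups. Section 5.7 uses these variables, with baseline dose, only as possible moderators of the treatment effect.
- Under Preliminary Analysis and Missing Data in 5.7, a covariate is added only if the arms, or completers and discontinuers, differ at baseline. It then enters as an auxiliary variable to support the missing-at-random assumption.

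Power Analysis and Sample Size in 5.7 claims adequate power for mediation with 300 participants, at alpha 0.05 and power 0.80, for small-to-medium paths. No numeric path is given.

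**The concern.** Randomisation protects the effect of condition on beliefs and the total effect of condition on each outcome. It does not protect the effect of month-3 beliefs on the outcome, because within each arm participants arrive at their beliefs for reasons that may also drive initiation, pain or opioid use. An autoregressor removes only what the baseline value of the same variable carries.

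Suppose more distressed Veterans hold worse month-3 beliefs, start treatment less often and have more pain at month 6. If CBT-TS also moves beliefs, both paths can reach significance with no effect of beliefs on anything. The model would report mediation, and later versions of the intervention might be built around the wrong target.

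The imbalance rule does not help. Its trigger is a difference between arms or between completers and discontinuers, whereas a confounder of this path can be perfectly balanced between arms. An auxiliary variable for missing data is also not an adjustment covariate in the outcome equation.

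**Working it through.** **1. The plan's own figure.** The 80% mediation power cannot be reproduced, because no paths, loadings or initiation rate are given. As a plausibility check, take equal standardised paths and require both to be significant at two-sided 0.05 with N = 300; the power is then the product of the two single-path powers:

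- paths 0.14: 0.685 × 0.675 = 0.46
- paths 0.18: 0.885 × 0.873 = 0.77
- paths 0.20: 0.941 × 0.931 = 0.88

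So 0.80 is plausible for paths a little above 0.18. That is power to detect a path; it presumes the path is unconfounded.

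**2. Size of the spurious path, continuous outcome.** From the documents: N = 300, 1:1, alpha 0.05. Assumed: all variables have variance 1; baseline distress U correlates 0.5 with baseline belief and with baseline outcome, which are otherwise unrelated; each autoregressive path is 0.5; condition moves belief by a standardised 0.20; U adds c to both month-3 belief and month-6 outcome; the true belief effect is zero.

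- Variance of U left after both baselines: each has regression weight 0.5/1.25 = 0.4, so R² = 2 × 0.4 × 0.5 = 0.4, leaving 0.6.
- Variance of month-3 belief given condition and both baselines: V = 0.6c² + [1 − (0.25 + c² + 0.5c) − 0.20²].
- Spurious coefficient: b = 0.6c²/V.
- Residual outcome variance: W = 0.6c² + [1 − (0.25 + c² + 0.5c)] − (0.6c²)²/V.
- Standard error: √(W/(300V)).

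For c = 0.3: V = 0.054 + 0.47 = 0.524; b = 0.054/0.524 = 0.103; W = 0.054 + 0.51 − 0.0056 = 0.558; standard error = √(0.558/157.2) = 0.0596; z = 1.73; chance of significance about 0.41. The condition-to-belief path is significant with probability above 0.99, so false mediation is about 41%.

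| c | V | b | z | False mediation, formula | Simulation, a = 0.14 to 0.26 | Simulation with baseline distress added |
|---|---|---|---|---|---|---|
| 0.1 | 0.656 | 0.009 | 0.15 | 5% | 4-6% | 4-6% |
| 0.2 | 0.594 | 0.040 | 0.68 | 10% | 9-10% | 4-5% |
| 0.3 | 0.524 | 0.103 | 1.73 | 41% | 35-42% | about 5% |

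The simulations used 3,000 replicates and the same joint-significance test. A separate simulation with 250 analysed gave about 4%, 10% and 26%. Hence about 5%, about 10% and roughly 25-40%.

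**3. Initiation.** Logistic model, N = 300, about 20% initiating (assumed), no true belief effect, autoregressors only. False mediation is about 7% (distress-to-belief 0.2, log odds ratio 0.3 in size), 10-11% (0.2, 0.5), 17-18% (0.3, 0.5) and 29-30% (0.3, 0.7). With baseline distress added it is 5-6%.

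**4. Cost in power.** With a true belief effect of 0.2 and no confounding, adding distress changes joint power from 0.734 to 0.733 (a = 0.14), 0.898 to 0.894 (a = 0.20) and 0.894 to 0.892 (a = 0.26).

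**The case against.** Much of the case on the other side stands.

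- The analysis is exploratory. Mediation appears in no aim or hypothesis in section 3.0. A reader might infer from the Introduction's sentence on how CBT works that the trial sets out to prove that mechanism. The documents do not support this: the sentence is cited background on CBT, and section 5.7 speaks of exploring potential mediators.
- A reader might also infer that the protocol itself names distress as a common cause. It does not. The statement that Veterans with pain "exhibit high rates of psychiatric and medical comorbidity, and are at increased risk of suicide" links comorbidity to neither beliefs nor initiation, and the Introduction elsewhere says that beliefs can drive negative emotions, which is the reverse direction. The support is narrower: the stated purpose of the anxiety and depression scores, the remark on loneliness, and the demographic differences in beliefs and in treatment use.
- It would be too strong to say that baseline pain is left out of the initiation equation. Section 5.7 examines the direct effects on initiation, pain and opioid outcomes in one model, with their autoregressors. Whether baseline pain also predicts initiation is unstated. Baseline distress is an autoregressor of none of the listed outcomes.
- The simulations are simpler than the planned model. Several belief instruments, including hopelessness and catastrophizing, may carry part of the distress signal at baseline. A re-run with 250 analysed, four baseline beliefs in each equation and baseline pain added for initiation lowered false mediation from 8-30% to 6-16% for pain and from 7-18% to 6-9% for initiation when the beliefs intercorrelate 0.25. At 0.5 the figures were 8-30% and 6-13%. The rates are also before the planned Benjamini-Hochberg adjustment.
- The return to about 5% after adjustment is built in, because distress was the only confounder simulated and was entered without error. It does not show that any covariate list suffices.

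None of this closes the path: the plan names no covariate set for it and no sensitivity analysis.

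**Conclusion.** The point holds for the exploratory mediation models. As written, they leave the path from beliefs to outcome adjusted only for baseline autoregressors, while plausible common causes already collected are used elsewhere or not at all. The direction of the risk follows from the design; its size does not. Under the assumptions shown it runs from negligible at residual distress effects of 0.1 SD to roughly 25-40% false mediation at 0.3 for a continuous outcome, and no figure in the documents says where in that range the trial lies.

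The randomised comparisons in Aims 1-3 do not depend on this path, and nothing here suggests they are biased. Severity is minor to moderate: the analysis is exploratory, but the plan gives it its own power claim and an experimental-therapeutics rationale, so a prespecified confounder set is a reasonable expectation.

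**What to change.** In 5.7, Exploratory Analyses, extend the sentence on autoregressors to say that every mediator equation and every outcome equation, including the one for initiation, also contains:

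- baseline PROMIS-29 anxiety and depression;
- baseline pain severity and interference;
- baseline MEDD;
- baseline loneliness;
- age, gender and race/ethnicity;
- psychosocial pain treatment before enrolment, from the record.

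These enter whether or not the arms differ on them. Use baseline values only: since the Introduction says beliefs can drive negative emotions, follow-up distress may lie on the causal path.

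Add a sensitivity analysis reporting, for each indirect effect, the residual mediator-outcome correlation that would bring it to zero. Report it as a quantity, not a pass/fail test, and describe all indirect effects as conditional on no unmeasured mediator-outcome confounding.

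The cost is wording, a few more parameters per equation and slightly more analysis work; the measures are already scheduled or in the record. The initiation equation is the tightest: at an assumed 20% initiating, 0.20 × 300 = 60 events would support at least ten covariates besides the beliefs, so the plan should say in advance how an unstable fit will be handled.

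Covariates will not settle one related matter: initiation by month 6 can occur before beliefs are measured at month 3.
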